Pittsburgh Sleep Quality Index (PSQI):A self-report questionnaire designed to assess sleep quality and disturbances over a 1-month time interval. Nineteen individual items generate seven subscale scores: subjective sleep quality, sleep latency, sleep duration, habitual sleep efficiency, sleep disturbances, use of sleep medications, and daytime dysfunction. A global score is obtained by summing the seven subscale scores (score range 0-21).

Insomnia Severity Index (ISI): A self-report instrument designed to assess insomnia according to criteria from the DSM-IV and the International Classification of Sleep Disorders that has been validated for clinical as well as research use 

Patient Health Questionnaire-9 (PHQ-9): The 9-item depression module of the PHQ, a self-report version of the PRIME-MD used to diagnose major mental disorders. The PHQ-9 items correspond with Diagnostic and Statistical Manual of Mental Disorders, 4th Edition (DSM-IV) criteria for depression, with each item scored from "not at all" to "nearly every day".

Alcohol Use Disorders Identification Test-Consumption (AUDIT-C): A 3-item modification of the AUDIT questionnaire that enquires about frequency and quantity of alcohol consumption in the past year, including frequency of episodes of heavy drinking, defined as six drinks in men and four drinks in women, per occasion. The AUDIT-C demonstrates excellent sensitivity and specificity for detecting heavy drinking, and is used in VA clinics as a standard screening tool for evaluating alcohol use. The gender-appropriate version of the AUDIT-C will be used as a secondary outcome measure to quantify the effect of prazosin on alcohol consumption. For administrations of the AUDIT-C subsequent to the baseline evaluation, the AUDIT-C will be modified to enquire about the past month, rather than past year alcohol consumption.

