**Statistical Analysis:** We will use summary statistics and graphs (e.g., strip charts, box plots, bar charts, scatter plots) to compare subject demographics at baseline by assigned treatment group (prazosin vs. placebo), and to initially compare outcomes by treatment group. Analyses will follow the intent to treat (ITT) principle. We will use a linear mixed effects model for the analysis of the primary outcome: 4-week frequency of moderate or severe HAs (Hypothesis 1a). We will have 4-week measures at four times during the course of the study: at Baseline, and at three different time points post-randomization (after 4, 8, and 12 weeks of steady-dose study drug). The response (dependent) variable will be 4-week frequency of moderate or severe HAs, and the predictor (explanatory) variables will include treatment group, week and a treatment group by week interaction term, along with the covariates site, gender, baseline age, baseline PSQI, time since onset of PTHAs, and analgesic use. A significant treatment group by week interaction term will indicate a significant difference in change from baseline between treatment groups. Results will include p-values, confidence intervals for change from baseline within each group, the confidence interval for difference in change from baseline between the two groups, and effect sizes.

We will also use linear mixed effects models for the secondary outcomes for Hypothesis 1b, i.e., 4-week average of: HA severity, number of hours of moderate to severe HA, individual HA duration, frequency of migraine days, frequency of non-migraine days, and frequency of use of abortive/analgesic medications (all obtained from the HA log); and for degree of HA-related disability (MIDAS and HIT-6). As for the primary outcome, secondary outcomes obtained from the HA log and the HIT-6 will have observations at four time points during the course of the study: Baseline and after 4, 8, and 12 weeks of steady-dose study drug; MIDAS will have observations at Baseline and week 12. The response (dependent) variable will be the secondary outcome, and the predictor (explanatory) variables will be the same as for the primary outcome.

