We will also use linear mixed effects models for the secondary outcomes for Hypothesis 2a, i.e., sleep quality and quantity, PTSD symptom severity, depressive symptoms, alcohol consumption, global cognitive function, health-related quality of life, and global clinical status. The schedule of study visits table shows when these outcomes will be measured during the study. The response (dependent) variable will be the secondary outcome, and the predictor (explanatory) variables will be the same as for the primary outcome and baseline PSQI will be omitted as a predictor variable in models measuring sleep quality and quantity.

For Hypothesis 2b, we will examine the correlations between within-subject change from baseline in HA parameters and within-subject change from baseline in sleep quality, PTSD symptom severity, mood, moderation of alcohol consumption, cognitive function, health-related quality of life, and global clinical status.

Linear mixed effects models easily accommodate missing values. We will compare the rate and timing of dropouts between treatment groups, and also look at graphs to assess the degree by which the prazosin and placebo groups differ in how the outcome variables relate to the predictor variables in order to assess issues related to missingness. If the pattern of missingness is disparate we will explore other methods of analysis such as multiple imputation.

**Data Management:** All study information will be recorded on standardized CRFs. Forms will be labeled with study code numbers only. Code numbers will be assigned sequentially, and will not include subject initials or any other personally identifiable information. Source documents, which may include identifying information, will be maintained in locked files within a locked office. The study coordinators at VA Puget Sound and Madigan will keep the key between the identity of participants and study code number. The key will not be shared with anyone other than members of the research team.

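### The AUDIT-C changes recall window after baseline, so within-arm alcohol change is confounded with questionnaire version and the between-arm comparison may lose precision

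*Combined protocol and SAP*

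**What the plan says.** Section 5.5 (Description of Study Measures) presents the AUDIT-C as a three-item form that "enquires about frequency and quantity of alcohol consumption in the past year". At every later visit, it adds, "the AUDIT-C will be modified to enquire about the past month, rather than past year alcohol consumption". The same entry says that the form "will be used as a secondary outcome measure to quantify the effect of prazosin on alcohol consumption". The Schedule of Study Visits places it at the Baseline Visit (T1) and at SD2, SD3 and SD4, so T1 has one recall window and all later visits have another.

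Section 5.6 analyses alcohol consumption under Hypothesis 2a with a linear mixed model in which "the predictor (explanatory) variables will be the same as for the primary outcome". In the primary-outcome model the baseline value is one of the repeated responses, and "A significant treatment group by week interaction term will indicate a significant difference in change from baseline between treatment groups". The results listed there include "confidence intervals for change from baseline within each group". The sample-size text states that secondary outcomes are handled like the primary. Hypothesis 2b correlates headache changes with "within-subject change from baseline in sleep quality, PTSD symptom severity, mood, moderation of alcohol consumption".

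Neither section describes a past-month AUDIT-C at baseline or any adjustment for the change of window.

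**The concern.** Moving follow-up to a one-month window is sensible. SD2 falls 4 weeks into the steady-dose period, after 5 to 7 weeks of titration, so about 9 to 11 weeks after T1. A past-year question there would cover 41 to 43 weeks of pre-drug time out of 52. What is missing is a matching baseline. The neighbouring measures whose windows are stated keep a single one: PSQI one month, HIT-6 the preceding month, MIDAS three months.

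Without that match, a participant whose drinking changed earlier in the year shows a change in score that has nothing to do with study drug. Three uses are exposed to different degrees: within-arm change, the Hypothesis 2b correlations, and the precision of the between-arm contrast. The first matters more than usual because Aim 2 and Hypothesis 2a speak of prazosin improving alcohol moderation without the comparison with placebo that Aim 1 spells out. That wording makes a within-arm reading easy to adopt.

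**Working it through.** **Inputs from the documents.** Past-year form at T1 and past-month form at SD2 to SD4 (5.5); 74 prazosin and 37 placebo completers, two-sided 5%, 80% power, effect size 0.57 on change (5.6).

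**Assumptions, because the documents give no AUDIT-C figures.** SD equal on both forms and set to 1; one follow-up; baseline/follow-up correlation r between 0.3 and 0.8; past-year scores higher than past-month scores by m, between 0 and 1 SD.

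**1. The plan's own figure.** 0.57 / √(1/37 + 1/74) = 0.57 / 0.2013 = 2.83. With 109 degrees of freedom the noncentral t gives 80.1% power, so the stated 80% reproduces. It is applied to secondary outcomes generally and is not specific to the AUDIT-C.

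**2. What the observed change contains.** Let Y0 be the past-year score at T1, M0 the past-month score at T1 (never collected) and M1 a later past-month score. Then

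M1 − Y0 = (M1 − M0) + (M0 − Y0).

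The second bracket is the window gap, −(m + e), with m common to everyone and e specific to the person.
- Within an arm, the mean is true change minus m. The two cannot be separated, because form and baseline status coincide.
- Between arms, the gap has the same expectation in both arms under randomization, so it cancels.
- In a 2b correlation, m drops out and e remains. It adds noise, or distortion if it is related to headache change.

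**3. Size of the within-arm effect.** Take no true change, no drug effect and r = 0.7. The SD of change is √(2 × 0.3) = 0.775, and its standard error in 74 participants is 0.775/√74 = 0.090. With m = 0.25 the ratio is 0.25/0.090 = 2.78. In 4,000 simulated trials per row:

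| m (SD) | apparent change, prazosin arm (SD) | within-arm test rejects | between-arm test rejects |
|---|---|---|---|
| 0 | 0.00 | 5% | 4% |
| 0.25 | −0.25 | 79% | 5% |
| 0.5 | −0.50 | 100% | 5% |
| 1.0 | −1.00 | 100% | 5% |

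**4. Precision between arms.** With baseline among the responses and a free arm effect, the arm-by-week contrast is essentially a comparison of change scores. Var(change) = 2·SD²·(1 − r), and the detectable difference is 0.57 × SD(change).

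| r | Var(change) | SD(change) | detectable difference (SD) |
|---|---|---|---|
| 0.8 | 0.4 | 0.632 | 0.36 |
| 0.7 | 0.6 | 0.775 | 0.44 |
| 0.6 | 0.8 | 0.894 | 0.51 |
| 0.5 | 1.0 | 1.000 | 0.57 |
| 0.3 | 1.4 | 1.183 | 0.67 |

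If the mismatch lowers r from 0.8 to 0.6, the detectable difference grows by √(0.8/0.4) = 1.41, or 41%. From 0.7 to 0.6 it grows by √(0.8/0.6) = 1.15, or 15%.

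**5. Options where only the past-year baseline exists (r = 0.6).**
- Change score with the mismatched baseline: 0.57 × √0.8 = 0.51 SD.
- Post-baseline scores alone: 0.57 SD.
- Post-baseline scores with the past-year score as covariate: 0.57 × √(1 − 0.36) = 0.46 SD.

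**The case against.** The strongest reply is that the question actually tested is safe. Hypothesis 2a is judged by the arm-by-week term, and a shift common to both arms leaves that term unbiased. This stands. A reader might infer that the alcohol treatment comparison is invalid, but the documents do not support that. Distortion would need a window gap that differs by arm among those analysed, for example through differential dropout, and nothing in the documents shows one.

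A reader might also infer that the plan expressly promises within-arm intervals for the AUDIT-C. It does not. Those intervals are listed for the primary outcome and reach alcohol only through the statement that secondary outcomes are treated alike. That carry-over is a fair reading, but it is not an explicit AUDIT-C commitment.

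Nor does the change of form by itself invalidate Hypothesis 2b, since a constant shift leaves a correlation unchanged. Only person-specific gaps matter, and the documents do not size them. Excluding substance use disorders other than caffeine and tobacco may narrow the range of drinking and so the gaps.

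Finally, every correlation and shift used above is an assumption. None of this removes the mismatch, which is plain on the text.

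**Conclusion.** The point holds in a limited form. Within-arm alcohol change cannot be read as change in drinking, because the recall window switches exactly when follow-up begins. At an assumed r of 0.7, a window shift of only 0.25 SD would make a null within-arm change appear significant in about 79% of trials. The 2b alcohol correlations carry person-specific noise or distortion of unknown size. The randomized contrast is unbiased by a common shift, but its detectable difference could rise by about 15% to 41% if the mismatch lowers r from 0.7 or 0.8 to 0.6. That range rests on equal SDs on both forms and on assumed correlations. One secondary outcome is affected. A wider reading that reaches the primary outcome or the numbers of 111, 160 and 228 has no support, since none of them depends on the AUDIT-C.

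**What to change.** Add the three past-month AUDIT-C items at the Baseline Visit (T1). Use that score as the baseline in the mixed model and in Hypothesis 2b, and keep the past-year form as a descriptor.

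For participants already enrolled without a past-month baseline:
- Compare post-baseline past-month scores between arms, with the past-year score as a covariate and not as a baseline response. Dropping the past-year score altogether would be less precise than the present plan (0.57 against 0.51 SD at r = 0.6), whereas using it as a covariate is more precise (0.46 SD).
- Name the between-arm difference to be tested, because without baseline among the responses the arm-by-week term no longer describes change from baseline.
- Report no within-arm alcohol change, and leave their alcohol change out of Hypothesis 2b.

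If few participants can still receive the new baseline, use the covariate analysis for everyone. The documents do not state enrolment status at the November 2021 version, so this choice should be recorded before alcohol data are examined by arm.

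The cost is three self-report items at one visit, a small CRF change, and an amendment submitted to both sites' IRBs.

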#### 5.6 Data Analysis

**Sample Size:** Our estimate of required sample size for the primary outcome is based on previous studies of chronic migraine HA, which reported standard deviations for change from baseline at 16 weeks in number of migraine days/month on the order of 5-6 days for both placebo and active drug groups, and a difference in change from baseline at 16 weeks in mean number of chronic migraine HA days/month between treatment groups of about 4 days (i.e., an effect size of about 0.67). An inclusion criterion for these studies was a minimum of 15 HA days/month, whereas the corresponding inclusion criterion for our proposed study is a minimum of 8 HA days/month. We therefore may see a smaller effect size. A trial with 111 completers (74 in the prazosin group, and 37 in the placebo group) yields 80% power to detect an effect size of 0.57 for a difference in change from baseline based on a standard two-sample t-test using a two-sided 5% Type I error level. Because we will be using linear mixed effects models to analyze this outcome, our power should be greater than 80% to detect an effect size of 0.57.

To arrive at the required number of participants to randomize, we are assuming a 30% dropout rate during the Titration and Steady-Dose Periods, based on the experience of Study Consultant [name] in other HA trials in the active-duty SM population. This dropout rate is due mainly to service-related events, such as reassignment or deployment, rather than to adverse drug effects. With a 30% dropout rate, we will need to randomize 160 participants who have met all eligibility criteria. Conservatively assuming a screen-fail rate of approximately 30% based on the Pre-Treatment Screening (e.g., meeting inclusion criteria for HA frequency/severity, adequate compliance with log keeping, voluntary study withdrawal, etc.), 228 potential participants will need to be recruited and enrolled to provide sufficient participants randomized for completion of the study.

The secondary outcomes will be analyzed in the same way as the primary outcome (i.e., using linear fixed effects models), so the power and sample size calculations are the same. For the secondary outcome: 4-week frequency of use of abortive/analgesic medications, Diener et al. saw a difference in change from baseline of 2.7 days (an effect size of 0.5) and Silberstein et al. saw a difference in change from baseline of about 1 day (an effect size of 0.2). For the secondary outcome: MIDAS, Diener et al. observed a difference in change from baseline of 29 (an effect size of 0.7), whereas Silberstein et al. observed a difference in change from baseline of 10 (an effect size of 0.2).

For the secondary outcome PSQI, we have information on the within-subject standard deviation and intraclass correlation (ICC) from our prazosin for combat-trauma PTSD study performed at Madigan/JBLM. For the PSQI, we observed a within-subject standard deviation of 2.5, an ICC of 0.6, and a difference in change from baseline between the prazosin and placebo group of 0.18 per week or 2.8 per 15 weeks (10 weeks at steady-dose). For the proposed study, we should have 80% power to detect a difference in change from baseline between the prazosin and placebo groups of 1.15 at 12 weeks of steady-dose study drug. For the secondary outcome measure PCL, we can use the results from the Clinician Administered PTSD Scale outcome from the prazosin for combat-trauma PTSD study as an approximation. For the Clinician Administered PTSD Scale, we observed a within-subject standard deviation of 13, an ICC of 0.7, and a difference in change from baseline between the prazosin and placebo groups of 0.75 per week or 11.3 per 15 weeks (including a 5-week titration period, thus 10 weeks of steady-dose). Based on the visit schedule, we will have 80% power to detect a difference in change from baseline between the prazosin and placebo groups of 5.25 after 12 weeks of steady-dose study drug. Note that the inclusion criteria for our prazosin for combat-trauma PTSD study required subjects to meet DSM-IV criteria for PTSD and have a score  $\geq$  5 (maximum score of 8) on the Clinician Administered PTSD Scale nightmare item, whereas the inclusion criteria for this study do not include these criteria so we do not expect to see as large effect sizes for PCL and PSQI.

**Statistical Analysis:** We will use summary statistics and graphs (e.g., strip charts, box plots, bar charts, scatter plots) to compare subject demographics at baseline by assigned treatment group (prazosin vs. placebo), and to initially compare outcomes by treatment group. Analyses will follow the intent to treat (ITT) principle. We will use a linear mixed effects model for the analysis of the primary outcome: 4-week frequency of moderate or severe HAs (Hypothesis 1a). We will have 4-week measures at four times during the course of the study: at Baseline, and at three different time points post-randomization (after 4, 8, and 12 weeks of steady-dose study drug). The response (dependent) variable will be 4-week frequency of moderate or severe HAs, and the predictor (explanatory) variables will include treatment group, week and a treatment group by week interaction term, along with the covariates site, gender, baseline age, baseline PSQI, time since onset of PTHAs, and analgesic use. A significant treatment group by week interaction term will indicate a significant difference in change from baseline between treatment groups. Results will include p-values, confidence intervals for change from baseline within each group, the confidence interval for difference in change from baseline between the two groups, and effect sizes.

We will also use linear mixed effects models for the secondary outcomes for Hypothesis 1b, i.e., 4-week average of: HA severity, number of hours of moderate to severe HA, individual HA duration, frequency of migraine days, frequency of non-migraine days, and frequency of use of abortive/analgesic medications (all obtained from the HA log); and for degree of HA-related disability (MIDAS and HIT-6). As for the primary outcome, secondary outcomes obtained from the HA log and the HIT-6 will have observations at four time points during the course of the study: Baseline and after 4, 8, and 12 weeks of steady-dose study drug; MIDAS will have observations at Baseline and week 12. The response (dependent) variable will be the secondary outcome, and the predictor (explanatory) variables will be the same as for the primary outcome.

We will also use linear mixed effects models for the secondary outcomes for Hypothesis 2a, i.e., sleep quality and quantity, PTSD symptom severity, depressive symptoms, alcohol consumption, global cognitive function, health-related quality of life, and global clinical status. The schedule of study visits table shows when these outcomes will be measured during the study. The response (dependent) variable will be the secondary outcome, and the predictor (explanatory) variables will be the same as for the primary outcome and baseline PSQI will be omitted as a predictor variable in models measuring sleep quality and quantity.

For Hypothesis 2b, we will examine the correlations between within-subject change from baseline in HA parameters and within-subject change from baseline in sleep quality, PTSD symptom severity, mood, moderation of alcohol consumption, cognitive function, health-related quality of life, and global clinical status.

Linear mixed effects models easily accommodate missing values. We will compare the rate and timing of dropouts between treatment groups, and also look at graphs to assess the degree by which the prazosin and placebo groups differ in how the outcome variables relate to the predictor variables in order to assess issues related to missingness. If the pattern of missingness is disparate we will explore other methods of analysis such as multiple imputation.

**Data Management:** All study information will be recorded on standardized CRFs. Forms will be labeled with study code numbers only. Code numbers will be assigned sequentially, and will not include subject initials or any other personally identifiable information. Source documents, which may include identifying information, will be maintained in locked files within a locked office. The study coordinators at VA Puget Sound and Madigan will keep the key between the identity of participants and study code number. The key will not be shared with anyone other than members of the research team.

The VISN-20 Northwest Network MIRECC ([name], Director; [name]) will supervise database design, double data entry, and any required computer programming. The MIRECC will provide maintenance of computer hardware and software at VA Puget Sound. Initial and second data entry will be performed at VA Puget Sound by the study Research Assistant under the supervision of the MIRECC Database Manager. The Database Manager will generate reports of data discrepancies. The study Research Assistant under the supervision of the Study Coordinators and Data Manager will be responsible for rectifying data entry errors within one week of discrepancy notification. Database maintenance includes nightly backup of hard drives and storage of backups at a safe off-site location. Only personnel having the correct user identification, PIN, and signing on from a computer with the appropriate IP address will have access.

